## 11. Efficacy

Efficacy analyses are part of the secondary objective of the study and will be on the assessments of Hgb and daprodustat dose over time. The Safety Set will be used for efficacy analyses.

### 11.1. Effect of Daprodustat on Hgb

The dose response of participants to daprodustat will be assessed by measurement of Hgb, where planned timepoints for all Hgb assessments are provided in the Schedule of Activities in Table 1. Hgb also serves to determine where a dose change is needed, see study protocol for details.

### 11.1.1. Analysis Methods

Similar to safety laboratory results, Hgb results will be obtained from local laboratories and entered into database by sites. Descriptive statistics (including number of observed Hgb values, number of missing Hgb values, mean, SD, and median of observed Hgb values) will be provided for the actual Hgb value at each study visit and change in Hgb from baseline at each subsequent study visits for all study participants for each sub-trial (D/ND). Additionally, the proportions of participants with Hgb above, within and below the target range (10 to 12 g/dL) will be summarized for each sub-trial (D/ND). No inferential testing will be performed.

Individual Hgb values will be plotted over time for each participant along with the corresponding daprodustat dose at each study visit.

All Hgb results will be displayed in a listing for each sub-trial (D/ND).

### 11.1.2. Handling of Unobserved Data

According Section 7.2, the following ICEs will be handled via while-on-treatment strategy.

- Permanent study intervention discontinuation due to any reason: any unobserved Hgb results
  after study intervention discontinuation will not be considered missing and will not be imputed;
  any observed Hgb results, if collected, will not be included for analysis.
- Unplanned use of ESA therapy: Hgb values within 8 weeks following the unplanned use of ESA
  therapy will be collected but will not be included in the analysis due to ESA's potential
  confounding effect on the interpretation of Hgb response; no imputation will be performed either.
- Intermittent use of rescue therapy (including use of iron supplements [oral/IV/both], blood transfusions and use of ESA and analogues): Hgb values from the date of initial use of rescue therapy until 8 weeks after the last dose of rescue therapy will be collected but will not be included in the analysis or imputed.
- Kidney transplantation or death: unobserved Hgb results after the event will not be considered
  missing and will not be imputed; any observed Hgb results, if collected, after kidney
  transplantation will not be included for analysis.

Disruption in study intervention, delays in study intervention, and transition to dialysis (for ND participants only) will be handled via treatment policy strategy where all observed Hgb results will be included for analysis, but no imputations will be performed for any missing Hgb results.

This document is confidential.

SAP Version: SAP V1.0 23-Jan-2025

Controlled Document ID: CC Effective Date 31-Aug-2020

Sponsor: GlaxoSmithKline Research & Development Limited; Protocol No.: 214066/Protocol Amendment 02

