#### **Brief Summary:**

The purpose of this study is to investigate the PK, safety and efficacy (Hgb response) of daprodustat in pediatric participants aged 3 months to less than 18 years with anemia associated with CKD (who will be studied sequentially in 4 decreasing age groups: 12 to <18 years, 6 to <12 years, 2 to <6 years and 3 months to <2 years).

All eligible participants will receive daprodustat for 52 weeks. PK assessments in the first 4 weeks of dosing are required in the initially recruited subset of participants in each age group (Integrated PK Phase) for each sub-trial (ND/D). These participants, who undergo the Integrated PK Phase, continue seamlessly with further dosing in the sub-trial, but further recruitment of their age group and the opening up of recruitment in the next sequential younger age group is prohibited until the data (PK, safety and Hgb response) from each Integrated PK Phase is analyzed, and no concerns for continuing the study as planned are detected.

Concomitant SoC therapy is permitted (with the exception of erythropoietin and its analogues), including iron supplementation at the discretion of the investigator to ensure iron replete status.

TMF-15144431 CONFIDENTIAL

214066 Protocol Amendment 02

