#### **Rationale for estimand:**

The primary interest lies in the safety of daprodustat for the treatment of anemia associated with CKD for the entire study duration; therefore, the treatment policy strategy is used regardless of disruptions in treatment, treatment delays, intermittent use of rescue therapy and/or unplanned use of ESA therapy, which reflect clinical practice. All safety data will be included up to the end of the period or up to the end of the follow-up period in the analysis irrespective of the occurrence of this ICE. Transition to dialysis (ND subtrial only) is also addressed with treatment policy strategy.

The secondary efficacy interest lies in the Hgb response to oral daprodustat for the treatment of anemia associated with CKD for the entire study duration; therefore, the treatment policy strategy is used regardless of disruptions in treatment or treatment delays, which reflect clinical practice. However, while-on-treatment strategy is used for the ICEs of intermittent use of rescue therapy and/or unplanned use of ESA therapy for the period of 8 weeks following the occurrence of the ICE, since these ICE may confound interpretation of Hgb response to daprodustat. Permanent treatment discontinuation for any reason is also addressed with while-on-treatment strategy.

Transition to dialysis (ND sub-trial only) is addressed with treatment policy strategy.

For participants who undergo a kidney transplantation, data will be considered up to the time of transplantation; therefore, this ICE is addressed with, while-on-treatment strategy. Such participants stop study intervention (daprodustat) and discontinue the study (see Section 7.2). Participants who die during the trial will be addressed with, while-on-treatment strategy.

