## 6.8.2. Standard of Care, including Iron Management

During the study (from Screening until the participant's final visit), investigators are expected to monitor the participant's overall clinical status to ensure standards of care are met to enable consistency of practice with KDIGO guidelines or local equivalent.

Iron status is checked regularly as per the SoA (Section 1.3). If iron deplete, the investigator should choose the route of administration and dose of iron based on the participant's iron status and local clinical practice. Investigators should be guided by local/regional guidelines; however it is strongly recommended that:

- Ferritin is maintained >100 ng/mL.
- TSAT is maintained >20%.
- Iron (excluding multivitamins) is not administered in the following situations:
  - o Ferritin >800 ng/mL and TSAT >20%, or
  - o TSAT >40%.

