#### For Anemia:

Rescue therapy may be needed if Hgb fails to respond adequately despite dose adjustment or the participant is unable to tolerate daprodustat.

If a participant has a low Hgb as a result of an acute or subacute event with an identifiable cause (e.g., GI bleed, blood loss due to surgery, vascular access or trauma), the treatment should be directed to the specific cause. Daprodustat should be continued at the current dose unless Hgb is >12.0 g/dL as a consequence of a blood transfusion, in which case according to Section 4.6, the daprodustat dose should be decreased (Hgb >12.0 to  $\leq$ 12.5 g/dL) or withheld (Hgb >12.5 g/dL) and Hgb checked again at the next scheduled study visit or at an extra study visit within the next 4 weeks if a study visit is not due in that time frame.

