#### 9.3.2.4. Tertiary Endpoints

#### Other Health Outcomes of Interest

During the study, the incidence of other health outcomes of interest listed below, will be presented using summary statistics (i.e., the number and percentage of participants) in each sub-trial (ND/D) overall and where appropriate within each age group.

- Related to Hgb and rescue therapy:
  - Use of iron supplements (oral/IV/both)
  - Blood transfusion
  - Use of rhEPO and analogues
- Related to changes in kidney function or intervention:
  - Transplantation
  - o ESKD (ND only)
  - o Switch between dialysis modalities (D only)
- Other:
  - o Death
  - All-cause hospitalization
  - Thrombosis (defined as: vascular access thrombosis, deep vein thrombosis or pulmonary embolism)
  - o All-cause loss of vascular access patency.

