# 5.5. Tertiary Other Health Outcomes of Interest

During the study, the incidence of other health outcomes listed below:

- Related to Hgb and rescue therapy:
  - Use of iron supplements (oral/IV/both)

This document is confidential.

SAP Version: SAP V1.0 23-Jan-2025

Controlled Document ID: Effective Date 31-Aug-2020

Filing requirements: TMF Page 21 of 59

Sponsor: GlaxoSmithKline Research & Development Limited; Protocol No.: 214066/Protocol Amendment 02

- Blood transfusion
- Use of recombinant human erythropoietin (rhEPO) and analogues
- Related to changes in kidney function or intervention:
  - Transplantation
  - Switch between dialysis modalities for D participants only
  - End stage kidney disease (ESKD) for ND participants only
- Other:
  - Death
  - All-cause hospitalization
  - Thrombosis (defined as: vascular access thrombosis, deep vein thrombosis or pulmonary embolism)
  - All-cause loss of vascular access patency.

Responses from Palatability and Acceptability Questionnaire include but limited to:

- Palatability rating (good, acceptable, neither good nor bad, bad, very bad).
- · Ease of swallowing (very easy, easy, neither easy nor difficult, difficult, very difficult).

This document is confidential.

SAP Version: SAP V1.0 23-Jan-2025

Controlled Document ID: CC Effective Date 31-Aug-2020

<sup>1 Unscheduled use of rhEPO or analogues is captured in the endpoint but should not be used as a rescue therapy.

<sup>2 ESKD is defined as at least one of the following:

• an estimated Glomerular Filtration Rate (eGFR), based on the Schwartz equation of <15mL/min/1.73m^2

· new kidney transplantation

the requirement for maintenance dialysis for ≥30 days

Page 23 of 59

Statistical Analysis Plan for Interventional Studies

Sponsor: GlaxoSmithKline Research & Development Limited; Protocol No.: 214066/Protocol Amendment 02

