# 7.2. Key Secondary Estimand

The secondary efficacy target estimand is the Hgb endpoints at each study time point in children and adolescents with anemia of CKD in each sub-trial (D/ND), regardless of disruptions or delays in study intervention whilst still continuing study intervention (daprodustat) and before any unplanned ESA therapy or rescue therapy.

- Population: Children and adolescent participants with anemia associated with CKD
- Variable: At each study timepoint:
  - Hqb value
  - Change in Hgb value from baseline
  - Hgb above, within and below the target range (10 to 12 g/dL)
- Population-level summary: At each study timepoint:
  - Summary statistics of Hgb value, including number of observed Hgb values, number of missing Hgb values, mean, SD, and median of the observed Hgb values.
  - Mean change in Hgb value from baseline, including number of observed Hgb values, number of missing Hgb values, mean, SD, and median.
  - Number and percentage of participants with Hgb above, below and within the target range (10 to 12 g/dL).
- Intercurrent events:

This document is confidential.

SAP Version: SAP V1.0 23-Jan-2025

Controlled Document ID: CC Effective Date 31-Aug-2020

Sponsor: GlaxoSmithKline Research & Development Limited; Protocol No.: 214066/Protocol Amendment 02

- Disruptions and delays in study intervention will be addressed using treatment policy strategy, where the treatment effect of interest is determined regardless of the occurrence of the ICE and no imputations will be conducted.
- Permanent study intervention discontinuation due to any reason will be addressed using while-on-treatment strategy, where unobserved Hgb results beyond study intervention discontinuation will not be imputed or included for analysis.
- Unplanned use of ESA therapy within the trial will be addressed using while-on-treatment strategy, where the Hgb values will be excluded for the period of 8 weeks following the occurrence of the intercurrent event from analysis and will not be imputed.
- Intermittent use of rescue therapy within the trial will be addressed with while-ontreatment policy strategy, where the Hgb values from the date of initial use of rescue therapy until 8 weeks after the last dose of rescue therapy will be excluded from analysis and will not be imputed.
- Kidney transplantation or death will be handled using while-on-treatment strategy, where
  data up the time of transplantation or death will be used for analysis, no missing Hgb

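### SAP 11.1.2 counts iron supplements as rescue therapy and drops the affected Hgb values from Tables 2.1 to 2.3, although the protocol manages iron as standard of care

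*SAP*

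**What the plan says.** SAP 11.1.2 lists the events handled by a while-on-treatment strategy for Hgb. One is "Intermittent use of rescue therapy (including use of iron supplements [oral/IV/both], blood transfusions and use of ESA and analogues". Hgb values from the first use until 8 weeks after the last dose are collected but neither analyzed nor imputed. The section presents itself as following SAP 7.2, which has the same window but says only "Intermittent use of rescue therapy within the trial", with no list of therapies.

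The protocol deals with iron elsewhere. The Brief Summary permits standard of care, "including iron supplementation at the discretion of the investigator to ensure iron replete status". Section 6.8.2, on standard of care and iron management, says that for an iron-deplete participant "the investigator should choose the route of administration and dose of iron based on the participant's iron status and local clinical practice". Rescue for anemia is a separate section, 6.8.3: "Rescue therapy may be needed if Hgb fails to respond adequately despite dose adjustment", or if daprodustat is not tolerated. Its sub-headings cover blood transfusion and the need for another ESA.

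Protocol 3.2 gives the estimand rationale: while-on-treatment handling applies to "intermittent use of rescue therapy and/or unplanned use of ESA therapy for the period of 8 weeks following the occurrence of the ICE", because these events may confound the Hgb response. Iron is not named there or in the attributes table.

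Iron and rescue therapy do meet in the tertiary outcomes (protocol Table 4 and 9.3.2.4, repeated in SAP 5.5 and 13.1). Iron, transfusion and rhEPO are listed there under "Related to Hgb and rescue therapy".

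**The concern.** The key secondary estimand describes Hgb on daprodustat. If iron is part of the care under which daprodustat is given, Hgb measured during and after iron belongs in that description. SAP 11.1.2 removes it. Any participant who takes qualifying iron then contributes fewer visits to Table 2.1 (Hgb by visit), Table 2.2 (change from baseline) and Table 2.3 (above, within and below target range).

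The exclusion can be triggered by following the protocol. Exclusion criterion 3 bars entry for ferritin below 25 ng/mL or TSAT below 20%, while 6.8.2 recommends keeping ferritin above 100 ng/mL. A participant with adequate TSAT and ferritin between those two values may enroll and then receive iron in line with 6.8.2.

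The change is also undeclared. Section 14 lists the loss of the age-group split and the dropped tertiary analyses, but nothing about the Hgb intercurrent events. The terms *intermittent* and *initial use* are not defined, so two programmers could flag different visits.

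**Working it through.** **The plan's own allowance.** No figure is given for iron. The nearest is the sample-size illustration (protocol 9.5.2, SAP 4.3): 60 × (1 − 0.17) = 49.8, taken as 50. The half-width is 1.96 × 1.4/√50 = 0.388 g/dL, or 0.398 with the t distribution on 49 df. Both round to the stated 0.4, so the figure reproduces. The documents do not say whether iron is inside the 17%. With four participants enrolled (population PK analysis plan supplied with the SAP, section 1.1), this allowance no longer describes the data.

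**Texts side by side.**
- Iron: named in SAP 11.1.2 as rescue; in protocol 6.8.2 as standard of care; absent from protocol 6.8.3, protocol 3.2 and SAP 7.2; not in Section 14.
- Transfusion: named in SAP 11.1.2 as rescue; in protocol 6.8.3 under rescue.
- ESA: named in SAP 11.1.2 as rescue; in protocol 6.8.3 as something to avoid, with its own sub-heading; SAP 5.5 footnote 1 says "Unscheduled use of rhEPO or analogues is captured in the endpoint but should not be used as a rescue therapy".

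Of the three therapies, iron is the only one the protocol manages wholly outside its rescue section.

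**Visits lost.** Protocol 4.6 schedules on-treatment Hgb at Weeks 2, 4, 8, 12, 16, 20, 24, 28, 36, 44 and 52: 11 visits, at days 14, 28, 56, 84, 112, 140, 168, 196, 252, 308 and 364 after Day 1. Nominal days are used and visit windows ignored. For iron from day s to day e, visit v is lost if s ≤ v ≤ e + 56.

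Single dose (s = e):

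| Dose day | Visits lost |
|---|---|
| 0–140 (Day 1 to Week 20), 141 days | 3 on 20 days (days 0–14, 28, 56, 84, 112, 140); 2 on the other 121 |
| 141–167, 27 days | 2 on all |
| 168–308 (Week 24 to 44), 141 days | 2 on the 4 visit days (168, 196, 252, 308); 1 on the other 137 |
| 309–364 | 1 (Week 52) |

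Examples: a dose at Week 5 (day 35) covers days 35–91 and loses Weeks 8 and 12. A dose at Week 29 (day 203) covers days 203–259 and loses Week 36 only.

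Courses (lengths assumed):
- Week 4 to 8: window Week 4 to 16; loses Weeks 4, 8, 12 and 16 = 4 of 11.
- Week 4 to 16: window Week 4 to 24; loses Weeks 4, 8, 12, 16, 20 and 24 = 6 of 11.
- Continuing to Week 52, only if that counts as intermittent use: from Week 4, 10 of 11; from Day 1, all 11.

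With iron out of the event, iron use removes 0 of 11.

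**What still shows the data.** Listing 16.17 gives all Hgb values and Listing 16.15 the concomitant therapy, which under SAP 9.6 includes iron. Table 3.6 summarizes hematology, including hemoglobin, by visit and as change from baseline on the Safety Set with no exclusion stated. Figure 2.1 plots individual Hgb; the SAP does not say whether the exclusion applies to it. Table 2.3 has no tabulated counterpart free of the exclusion.

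**The case against.** The protocol is not a clean baseline. Its tertiary heading puts the same three therapies together, with the same oral/IV/both wording, so 11.1.2 may simply fill in an undefined term from the protocol's own grouping. Section 6.8.3 does not claim to be exhaustive. Footnote 1 of SAP 5.5 carves out only rhEPO, which could imply that iron and transfusion may be rescue. Silence in the estimand texts proves little, since they do not name transfusion either. Nor does investigator discretion separate iron from rescue, because 6.8.3 also leaves rescue to the investigator. Whether iron confounds Hgb or belongs to the treatment setting is an estimand choice.

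Much of this stands as explanation. The heading is the likely source of the wording, and the silence is not decisive alone. But a heading over an outcome list does not define an intercurrent event. What distinguishes iron from transfusion is that the protocol puts one under standard of care and the other under rescue. An estimand choice that widens the event should be stated in SAP 7.2 and Section 14, and it is in neither.

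The protocol has its own flaw here. The attributes table in 3.2 writes the Hgb window for rescue therapy in terms of unplanned ESA only, so it cannot settle what rescue covers.

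A reader might also infer that the iron rule makes Tables 2.1 and 2.2 disagree with Table 3.6. Iron would add to the difference, but 11.1.2 also excludes Hgb after discontinuation, ESA, transfusion and transplantation, so the tables can differ with iron removed.

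**Conclusion.** The inconsistency is real and worth correcting. SAP 11.1.2 widens the rescue-therapy event to include iron, without support in the estimand texts and without declaring it. For a participant who takes qualifying iron, the loss is 1 to 3 of 11 visits for one dose and 4 to 6 for an assumed 4- to 12-week course from Week 4. These counts rest on nominal visit days.

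Two stronger readings are tempting and not supported. The first is that iron users lose nearly all their Hgb data: the 10- and 11-visit losses need continuing iron to count as *intermittent*, which is not its natural sense, and the *within the trial* wording in 7.2 may point away from iron already running at Day 1. The second is that the tables will be distorted, or reduced to one participant at a visit: no iron-use rate and no D/ND split is given for the four participants, so the effect could be nil.

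The harm is limited to three descriptive secondary tables. There is no inferential testing, and Listings 16.15 and 16.17 let a reader recover the iron use and all Hgb values.

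**What to change.** 1. In SAP 11.1.2, remove iron supplements from the rescue-therapy event. State there and in 7.2: *Iron supplementation is standard of care and is handled with a treatment policy strategy; Hgb values during and after iron use are included.*
2. If the sponsor intends the exclusion, list it in Section 14, define which iron use counts (iron already running at Day 1, continuing iron, repeat courses) and add an iron-included version of Table 2.3.
3. In either case, footnote Tables 2.1 and 2.2 to say which Hgb values are excluded relative to Table 3.6, since the other 11.1.2 exclusions also make them differ.
4. In either case, reconcile the ESA-only rescue window in the protocol 3.2 attributes table with SAP 7.2.

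Cost: text edits, one derivation flag and two footnotes; if the exclusion is kept, also a Section 14 entry and one extra table. No new data are needed, because iron use is already collected and listed (SAP 13.1).

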#### 11.2. **Dose Change Over Time**

The other secondary efficacy analysis will be based on the required daprodustat dose over time, where descriptive statistics (mean, SD, and median) for daprodustat dose at each study visit will be summarized for each sub-trial (D/ND).

Individual daprodustat dose over time for each participant will be plotted along with the corresponding Hgb results at each study visit.

This document is confidential.

SAP Version: SAP V1.0 23-Jan-2025

Controlled Document ID: CCI Filing requirements: TMF Effective Date 31-Aug-2020

Sponsor: GlaxoSmithKline Research & Development Limited; Protocol No.: 214066/Protocol Amendment 02

## 12. Pharmacokinetics

Blood samples for pharmacokinetic (PK) analysis of daprodustat and its metabolites (GSK2391220 [M2], GSK2531403 [M3], GSK2487818 [M4], GSK2506102 [M5], GSK2531398 [M6], and GSK2531401 [M13]) will be collected at the time points indicated in Table 1 — Schedule of Activities. The actual date and time of each blood sample collection will be recorded. The timing of PK samples may be altered and/or PK samples may be obtained at additional time points to ensure thorough PK monitoring. Details of PK blood sample collection (including volume to be collected), processing, storage and shipping procedures are provided in the SRM.

Plasma analysis will be performed under the control of Bioanalysis, Immunogenicity, and Biomarkers - In Vitro/In Vivo Translation Platform/Scinovo, GlaxoSmithKline, the details of which will not be covered in current document but will be included in the SRM. Concentrations of daprodustat and its metabolites (GSK2391220 [M2], GSK2531403 [M3], GSK2487818 [M4], GSK2506102 [M5], GSK2531398 [M6], and GSK2531401 [M13]) will be determined in plasma samples using the currently approved bioanalytical methodology. Raw data will be archived at the bioanalytical site (detailed in the SRM).

A PK dataset will be delivered to GSK for PK analysis and will comprise substituting NQ values as follows:

- If one or more non-quantifiable (NQ) values occur in a profile before the first measurable concentration, they will be assigned a value of zero concentration.
- If NQ values occurs between measurable concentrations or after the last measurable concentration in a profile, the NQ values will be set to ½ LLQ

